- (ii) Participants have comorbidities (a) developmental impairment (b) learning disability, (c) personality disorders, and/or (d) any clinically significant medical diseases (by case-file review).
- (iii) Participants have organic psychosis or a primary drug or alcohol addiction.

Randomisation and recruitment procedure

Participants referred to the study by ICCMW will be assessed at a screening examination to ensure eligibility and obtain written consent by a research assistant. Eligible participants will undertake a further interview on outcome measures prior to randomization within 3 weeks the commencement of intervention. In order to avoid the contamination of participants, participants allocated to either treatment or control groups will be reminded not to share what they have experienced in the group work among members in the service organization. The subjects will mainly be recruited from three service organizations and thus around 35 from each organization in proportion to the total number of potential participants. Participants will be randomly assigned to receive Mindfulness-based Cognitive Therapy for Psychosis (MBCTp) plus TAU or TAU plus Psychoeducation for Psychosis (PEp). Simple randomization will be used to select subjects from the patient list in each organization to ensure that each participant will have equal opportunity to be included into the study (Altaman and Bland, 1999). A computer-based program (simple randomization) will be used to aid the randomization procedure. Assignment to the study groups will be made independently of staff involved in the recruitment and management of participants in the study. Raters who collect follow-up data will also be blind to the identity of participants. Considerable efforts will be made to ensure the blindness of raters such as storage of data will be kept separate from the therapists and raters who will be working in different rooms. All data will be locked in a cabinet with limited access only by responsible raters and recorded in a logbook.

Sample size

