Sample size has been estimated on the basis of previous clinical trials of mindfulness interventions for people with psychosis, in which the primary outcome of depression and anxiety (effect size=0.76), and distress relating to psychotic symptoms (effect size=0.50) were the main outcomes (White et al., 2011; Chadwick et al., 2016). Study power calculation indicated that 82 participants (n=41 per group) were required to detect statistically significant differences on emotional distress between two groups with effect size of 0.63 at post-intervention, p=0.05 and power of 0.80 (Stevens, 2009). Taking account of a 15% attrition, the total sample size required should be 95 (n=48 per group).

Interventions

MBCTp will be delivered to the study groups while PEp will be delivered to the control groups. Intervention groups will be facilitated by the researcher who is experienced in cognitive therapy and mindfulness. The psychoeducation group will be conducted by a research assistant (RA1) who is an experienced psychiatric nurse and is trained by the researcher and an experienced psychoeducation researcher. All sessions will consist of 12-weekly 1.5- hour sessions, plus 12-week practice at home with guided CDs which comprises short mindfulness practice (Chadwick et al, 2016). Mindfulness practice will be with guided verbal instructions offered every couple of minutes to avoid prolonged silence. Mandatory individual home practice will be devised and completion of homework will also be assessed by counting the number of submissions and percentage of

completion per program. The session content will be protocolled according to the origins of MBSR (Kabat-Zinn, 2013) and MBCT (Teasdale, Williams and Mark, 2014) (Appendix 1). It will also be validated by a panel of experts including psychiatrists, clinical psychologists and psychiatric nurses who are experienced in mindfulness and cognitive therapy. Psychoeducation (psychosis) (PEp) will be developed based on the manuals produced by the Early Psychosis Prevention and Intervention of the Early Psychosis Prevention and Intervention Centre (EPPIC) National Support Program (ENSP), Australia and the psychoeducation manual produced by the Foundation for Life Sciences, University of Technology Sydney, Australia (Creek et al, 2015; Perry et al, 2012). It will be validated by a panel of experts and previewed by 5-10 service users in the pilot study.

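### Simple randomization, with no organization term in the analysis, leaves arm sizes and balance by organization to chance; stratified blocks would be a cheap improvement

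*SAP*

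**What the plan says.** Under Randomisation and recruitment procedure, the SAP names the allocation tool: "A computer-based program (simple randomization) will be used to aid the randomization procedure". The next sentence keeps assignment independent of the staff who recruit and manage participants. An earlier sentence in the same section uses the same term for a different step: "Simple randomization will be used to select subjects from the patient list in each organization". That sentence goes on to speak of an equal opportunity of being included, which is the language of sampling rather than of assignment to arms. No block, stratum or minimisation is mentioned anywhere.

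On recruitment, the section says: "The subjects will mainly be recruited from three service organizations and thus around 35 from each organization".

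Under Sample size, the plan assumes equal arms: "82 participants (n=41 per group) were required to detect statistically significant differences on emotional distress between two groups". The inputs are a standardized effect of 0.63, a 5% significance level and 80% power. It then allows for 15% attrition and arrives at 95 in total, given as 48 per group.

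Under Interventions, both treatments are given in groups: "MBCTp will be delivered to the study groups while PEp will be delivered to the control groups". The number, size and location of those groups are not stated.

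Under Data Analysis, the comparison of outcomes is a repeated-measures ANOVA within and between groups and across three post-tests. Organization is not named as a factor.

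**The concern.** The sample size rests on equal arms, and the participants come from three separate services. Simple randomization behaves like a coin toss for each person, so at about 95 people it can leave the arms visibly unequal, both overall and within an organization. If outcomes differ between organizations through service or case mix, a chance imbalance adds noise to the treatment contrast. With no organization term, the planned model cannot remove that noise. At stake are some precision and the credibility of the comparison in the one trial that is run. The validity of the test is not at stake.

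**Working it through.** **Inputs.** From Sample size: standardized effect 0.63, alpha 0.05, power 0.80, 41 evaluable per arm, 15% attrition, total 95, or 48 per arm. From Randomisation and recruitment procedure: three organizations of around 35. Assumptions: a two-sided test (sidedness is not stated) and 1:1 allocation (implied by the equal group sizes).

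The totals do not agree exactly (95; 2 × 48 = 96; 3 × 35 = 105), so each is used below.

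**1. The plan's own figure.** A two-sided two-sample t-test at d = 0.63 and 80% power needs 40.5, hence 41 per arm, and power at 41:41 is 80.5%. The stated 82 is reproduced. For attrition, 82 × 1.15 = 94.3, which rounds up to 95. Dividing instead, 82 / 0.85 = 96.5, or 97. The difference of 2 has no bearing here.

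**2. Arm sizes.** The size of one arm is Binomial(N, 0.5).

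| N | 95% range, one arm | P(arms differ by 10 or more) | P(as equal as possible) |
|---|---|---|---|
| 95 | 38 to 57 | 30% | 16% (47:48) |
| 96 | 38 to 58 | 36% | 8% (48:48) |
| 105 | 42 to 63 | 33% | 15% (52:53) |

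**3. Balance within an organization.** With 35 people, one arm is Binomial(35, 0.5), with a 95% range of 12 to 23.

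- P(one organization splits 13:22 or worse) = 0.175. For at least one of three: 1 − (1 − 0.175)³ = 0.44.
- P(one organization splits 12:23 or worse) = 0.090. For at least one of three: 1 − (1 − 0.090)³ = 0.25.

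**4. Power.** The noncentrality is 0.63 × √(n₁n₂/(n₁ + n₂)), with n₁ + n₂ = 82 throughout so that only the split changes.

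- 41:41 gives 0.63 × √20.5 = 2.85, power 80.5%.
- 35:47 gives 0.63 × √20.06 = 2.82, power 79.6%.
- 32:50 (the edge of the 95% range at 82) gives 0.63 × √19.51 = 2.78, power 78.5%.
- Averaged over Binomial(82, 0.5), power is 80.0%, a mean loss of about 0.5 percentage point.

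**5. Noise from organization imbalance.** The SAP gives no between-organization variance, so assume that organizations explain a share ρ of the outcome variance. Take three organizations of 32, to match 48 per arm. The difference between arms in one organization's share has variance of about 32/48² = 0.0139. The three differences sum to about zero, which brings in a factor 2/3. The chance shift in the treatment contrast, in outcome-SD units, therefore has SD √(ρ × 3 × 0.0139 × 2/3) = 0.167√ρ.

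- ρ = 1%: 0.017
- ρ = 5%: 0.037
- ρ = 10%: 0.053

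The sampling error of the contrast at 41 per arm is √(2/41) = 0.22.

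**The case against.** The strongest reply is that simple randomization is a legitimate method. It is unbiased, the test remains valid whatever split occurs, 48 per group is a planning target, and blocking details often sit in a protocol. Much of this stands, and it keeps the point modest. The protocol argument does not remove it, because the SAP does name a method, and that method is the unrestricted one.

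Several stronger readings are tempting, and the document does not support them:

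- A reader might infer a serious loss of power. The plan's own inputs give about half a percentage point on average, and about two at the edge of the 95% range.
- A reader might infer that organization differences bias the result. Chance imbalance adds variance, not systematic bias. Even if organizations explained 10% of the variance, the added noise would have SD 0.053 against a sampling error of 0.22.
- A reader might infer unequal therapy groups within each organization. The instruction to both arms not to share group experiences within the service suggests that both arms coexist there. The SAP does not say where groups are formed or how large they are, and the number of groups could vary instead of their size. It also offers nothing on whether group size affects outcome.
- A reader might take the sentence on selecting from each organization's patient list as further proof of unrestricted allocation. It concerns who is selected, not which arm they enter.

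**Conclusion.** The point holds as a cheap improvement. The SAP states unrestricted allocation for a trial planned with equal arms in three organizations, and its analysis has no organization term. Visible imbalance is likely: about a one-in-three chance that the arms differ by 10 or more, and a 44% chance that at least one organization splits 13:22 or worse. The consequence is small: limited noise and a mean power loss of about 0.5 point. What would be gained is mainly balance by organization, with some precision.

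These figures assume 1:1 allocation, a two-sided test and, for the within-organization splits, 35 people in each of three organizations. How much organization balance matters depends on a between-organization variance that the SAP does not give.

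**What to change.** In Randomisation and recruitment procedure, replace simple randomization as the method of allocation with computer-generated permuted blocks of randomly varying size, stratified by organization. Conceal the list and have it held outside recruitment. State separately how participants are selected from the organizations' lists, so that one term no longer covers both steps.

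In Data Analysis, include organization as a factor in the primary model. If allocation has already begun, prespecify that term before the data are analysed.

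The cost is a setting in the allocation program and one model term, with no extra participants or visits. The downside is slight predictability at the end of a block. Varying block sizes and the independent assignment that is already planned limit this.

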The WHOQOL-100 (Li, Young, Xiao, Zhou and Zhou, 2004) which is a self-administered questionnaire consisting of 100 items and among them, there are six domains: physical, psychological, level of independence, social relationship and environmental and spirituality. The internal consistency is acceptable ($\alpha=0.76 - 0.90$ across domains) and the validity is strong ($\alpha = 0.72 - 0.82$) across all domains.

Positive and Negative Syndrome Scale (PANSS) (Kay, Fiszbein and Opler, 1987; Kay, Fiszbein and Opler, 2007) is a 30-item, 7-point scale measuring positive and negative syndrome, differentiation of clinical symptoms and severity of illness. The seven rating points represent increasing levels of psychopathology from 1 (absent) to 7 (extreme). The PANSS ratings will be derived from clinical interview, clinical reports or family members over the past one week. The overall alpha coefficients for the Positive and Negative Scales are 0.73 and 0.83 ($p<0.001$) respectively.

Acceptance and Action Scale (AAQII) (Bond et al., 2011). A seven-item questionnaire that is a commonly used self-report measure of experiential avoidance which also measures psychological inflexibility. The items are rated on a 7-point Likert scale from 1 (never true) to 7 (always true). Its internal consistency is $\alpha=0.78 - 0.88$, while test-retest reliability is 0.81 and 0.79 for 3 and 12 months respectively. The internal consistency of a Chinese translated version for college students and athletes is $\rho= 0.88$ and $\rho=0.85$ respectively. The test-retest reliability is $\gamma=0.86$ and $\gamma=0.74$ across an average period of one month for college students and athletes (Zhang et al, 2014).

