Five Facet Mindfulness Questionnaire (FFMQ) (Baer et al, 2006) is a 39-item self-report questionnaire that measures five facets of mindfulness: observing; describing; acting with awareness; non-judging and non-reacting. The internal consistency for each of the five facets are $\alpha=0.83$, $\alpha=0.91$, $\alpha=0.87$, $\alpha=0.87$ and $\alpha=0.75$ accordingly. Items are scored on a 5-point Likert scale ranging from 1 (never or very rarely true) to 5 (very often or always true). The Chinese version of the Five Facet Mindfulness Questionnaire (FFMQ-C) obtained a good test-retest reliability (0.88) and a high internal consistency (0.83 in the community sample and 0.80 in the clinical sample) (Hou, Wong, Lo and Mak, 2013). A short form scale of the FFMQ (FFMQ-SF) is highly and significantly correlated with the FFMQ-C ($r=0.96$), and explained 91.3% of the variance of the FFMQ-C which will be adapted for the purposes of the study.

The last outcome assessment will be the number and length of re-hospitalization referenced from the case files and self-reporting.

Regarding the qualitative data obtained by focus group interviews, it will be used to determine the common themes being mentioned most frequently by participants and organized under different categories such as expectations, positive and negative outcomes, personal difficulties, positive and negative comments about the program and description.

Data collection procedure

There will be two research assistants (RA), RA1 will be responsible for conducting the psychoeducation program and RA2 will be blinded and doing data collection. The RA2 will conduct the baseline measurements after obtaining the written consent and following comprehensive explanations about the study purpose and procedure and its ethical issues. After that, the participants will be assigned randomly to either study group or control group. Patients' outcomes at the ICCMWs will be measured at one week post-intervention using the same set of questionnaires as the baseline measures.

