Two groups of 3-4 participants in treatment group will be interviewed in a quiet interview room in the ICCMWs, or as preferred by the participants. Participants with significant positive changes, minimal changes and negative changes will be invited according to the baseline and Post-test 1 measurement. Interviews in a focus group format will be conducted to identify the strengths and limitations and therapeutic components from the participants' perspective. Interview questions will be developed based on an open and broad basis criterion (Appendix 2). Audio-recorded group sessions will also be used to examine the group process/dynamics and participants' involvement and appraisals of the group program.

The outcome measurements will be completed by the participants at three and six months after the interventions with the help of RA1 who will be blind to the participants' assigned groups. By self-reporting or case files reviewing, re-hospitalizations of the participants will also be examined and calculated and checked against their medical records. Participants' recruitment, interventions, data (outcomes) collection, and data analyses are outlined in a flow diagram of Appendix 3, as recommended by the latest CONSORT statement.

Data Analysis

Intention-to-treat (ITT) analyses (Fisher et al, 1989) will be used to provide a more conservative estimate of outcomes. By using IBM SPSS, version 23.0, all data on participants' socio-demographic illness-related characteristics, attendance and completion rate, and study outcomes will be numerically coded, summarized and analyzed. Repeated-measures ANOVA tests will be used to assess any significant differences on all dependent (outcome) variables within and between groups and across three post-tests (one week, 3 months and 6 months follow-up).

Sub-group analysis for participants who will complete all sessions and those completers, and the outliers which can have deleterious effects on statistical analyses will also be screened. Defined completers will be those who have attended at least eight sessions by which the main themes of the program are covered (Nose, Barbui and Tansella, 2003).

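### Rater masking is defined by participant identity instead of allocation, and allocation is not adequately protected for PANSS

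*SAP*

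**What the plan says.** All references are to the SAP.

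- **Randomisation and recruitment procedure**, on masking: "Raters who collect follow-up data will also be blind to the identity of participants". The next sentence gives the means: "Considerable efforts will be made to ensure the blindness of raters such as storage of data will be kept separate from the therapists and raters", with therapists and raters also working in different rooms.
- **Same section**, on silence: to avoid contamination between arms, participants "will be reminded not to share what they have experienced in the group work among members in the service organization". No instruction concerns what they or their relatives may say to a rater.
- **Outcome Evaluation**: "The PANSS ratings will be derived from clinical interview, clinical reports or family members over the past one week". The rater is not named.
- **Data collection procedure**, on staff: "RA1 will be responsible for conducting the psychoeducation program and RA2 will be blinded and doing data collection". Later in the same section, participants complete the 3- and 6-month measurements with help from RA1, who is described there as unaware of group assignment. The **Interventions** section confirms that RA1 conducts the psychoeducation groups.
- **Same section**, on admissions: "By self-reporting or case files reviewing, re-hospitalizations of the participants will also be examined and calculated and checked against their medical records". It does not say who does this or when.

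**The concern.** The masking sentence names the wrong property. Whoever interviews a participant, talks to the family or reads that person's reports knows who the participant is. The fact to conceal is the arm.

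This matters most for PANSS. DASS-21, ERQ, WHOQOL-100, AAQII and FFMQ are answered by participants who know which programme they attended. PANSS is the only scale scored by a rater, and it carries the aim that less distress will improve positive and negative symptoms. A PANSS deterioration of 25% or more is also a reporting trigger under Adverse events reporting and monitoring. A rater who knows the arm may, without intending to, score toward the expected result.

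The assistant who delivers the control programme is also named as a blind helper at two of the three post-tests. There the problem may extend beyond PANSS, because RA1 helps participants complete the measurements, which include the primary DASS-21.

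**Working it through.** No figure in the plan bears on this point, so the check sets the passages side by side.

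**1. Which property is promised?** One sentence promises blindness to identity. The Data collection procedure section speaks of blindness to group assignment. Only the second is possible for a PANSS rater, and only the second guards against bias.

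**2. Which routes to the arm are closed?**

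| Route to the rater | Measure in the SAP |
|---|---|
| From therapists | Different rooms; RA2 separate from those delivering the programmes |
| From stored data | Separate storage, limited access |
| From the participant | None; the reminder concerns fellow members |
| From a relative | None |
| From a clinical report | None |
| From the assessor's own work | RA2 has no therapist role, but RA1 is named at 3 and 6 months |

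**3. Would disclosure be informative?** Attendance alone would not be: both arms have 12 weekly sessions of 1.5 hours. Content would be. Appendix 1 gives body scans and sitting meditation in one arm, and diagnosis, medication and involuntary treatment in the other. One remark about content during an interview can identify the arm. Relatives may notice mindfulness practice at home, and a report from the referring service may name the programme. Both are assumptions; the SAP states neither.

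**4. Is the PANSS source fixed?** No. The three sources are joined by *or*, with no rule for choosing. The source may therefore differ between visits, participants or arms, and so may exposure to the open routes.

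**5. Who assesses?** The post-tests are at one week, 3 months and 6 months. If RA2 collects data throughout, all three are covered by a blinded person. If RA1 assists at 3 and 6 months, two of the three involve someone who knows who attended the psychoeducation groups. RA1 can then largely infer that the others are in the mindfulness arm, except for control participants who never attended. The two statements cannot both stand.

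**6. How large is the bias?** The document gives neither the proportion of raters unmasked nor the resulting shift in score. Purely as illustration, bias = proportion unmasked × shift in those cases. With assumed values, 0.25 × 0.2 = 0.05 SD and 0.5 × 0.3 = 0.15 SD. These products restate their assumptions and are not estimates for this trial.

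**The case against.** A reader might infer that masking of PANSS is bound to fail. The document does not support that. Knowing a participant's identity does not reveal the arm, session number and length are the same in both arms, and disclosure by participants, relatives or reports is possible but not certain.

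A reader might also picture one rater who uses all three PANSS sources and then checks the case files. The SAP lists the sources as alternatives, names no PANSS rater, ties file review to re-hospitalization, and does not say who performs it.

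The intention is also clear enough. Other sentences speak of group assignment and of a blinded RA2, and assignment is made independently of recruiting and managing staff. On that reading *identity* is a slip of wording, and naming RA1 at 3 and 6 months may be a slip for RA2. Finally, informant rules and the order of file access are often left to a protocol, which is not at hand.

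Most of this stands, and it limits the point to inadequate protection. It does not remove the point. This document itself sets out the masking and its safeguards, misnames what is masked, limits the reminder to fellow members, and gives conflicting roles to RA1. Good intentions elsewhere in the text do not close the open routes.

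**Conclusion.** The point holds in limited form. The SAP should mask allocation and says identity. Its safeguards separate raters from therapists and stored data but leave disclosure by participants, relatives and reports unaddressed. The PANSS source is not fixed. The RA1 and RA2 statements contradict each other for two of three post-tests; as written, RA1 cannot be blind there, though the SAP does not say that RA1 scores PANSS.

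The main exposure is a secondary outcome. The primary DASS-21 is touched only so far as RA1's help could influence participants' answers. The direction of any bias would plausibly favour the expected result, but its size cannot be estimated from the document. This is an inexpensive improvement worth making, and it does not show that the PANSS results will be invalid.

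**What to change.** 1. In Randomisation and recruitment procedure, replace *identity* with *allocation*.
2. Reconcile the RA1 and RA2 statements in Data collection procedure so that the blinded RA2, already named, is the assessor at all three post-tests. Name the PANSS rater.
3. Extend the existing reminder: participants and relatives are asked not to mention their group or its content to the rater.
4. Set one PANSS source rule for all visits and both arms, and complete PANSS before any case file or report is opened. Do the re-hospitalization check afterwards and say who does it.
5. Record any unmasking at each post-test, with how it occurred, and report it by arm. An actual event is easier to interpret than a guess of allocation, which apparent improvement can drive.

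The cost is a few sentences and one field on the PANSS form. No extra staff are needed, although the 3- and 6-month work now given to RA1 passes to RA2. The downside is that PANSS makes slightly less use of file information.

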The present study is the first randomized controlled trial of group mindfulness-based intervention for psychosis. We hypothesize that mindfulness will have a positive impact on emotion regulation and distress and in so doing this will have a positive impact on psychotic symptoms, quality of life and re-hospitalization. The primary outcome will be a measure of emotional distress. The primary hypothesis will be group Mindfulness-based Cognitive Therapy for Psychosis (MBCTp) plus treatment-as-usual (TAU), in comparison to active control group psychoeducation plus TAU, will lead to adaptive processing of emotion in people with psychotic disorders and consequently alleviate distress in response to psychotic symptoms.

Management of psychosis

According to Chien and Yip's (2013) comparative review of the current pharmacological, medical treatments and psychosocial interventions for schizophrenia, first –and /or second-generation antipsychotics have remained the first-line medical treatment for psychosis. Such interventions have shown to be effective in reducing overall psychotic symptoms and relapse in patients with schizophrenia, at least in the short-term or at the acute stage of illness. However, the use of antipsychotics alone has its limitations in tackling the frequency of negative symptoms, cognitive impairments, stressful life events and psychological distress, as well as those illness-related and drug-induced problems such as weight gain. It has been recommended that psychological or psychosocial interventions should be considered as an adjunct to antipsychotic agents such as cognitive therapy, psychoeducation, family intervention, social skills training and assertive

community treatment (The National Institute For Health and Care Excellence, 2014). Application of such interventions to people with psychosis has shown satisfactory levels of short- to medium-term clinical efficacy in terms of symptom control or reduction, level of functioning, and/or relapse rate (Chien, Leung, Yeung and Wong, 2013) when used alongside antipsychotics.

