To ensure treatment fidelity, three to four sessions will be randomly audio-recorded per intervention group to make up a full program for progress evaluation and commented by an experienced psychiatrist who has been practicing mindfulness and cognitive therapy for over 10 years based on the validated manualized protocol and the Mindfulness-Based Interventions Teaching Assessment Criteria (MBI:TAC) (Crane et al, 2013). The attendance and dropping-out of patients in both treatment and active control group will be continuously monitored by the researcher.

Outcome Evaluation

The primary outcome will be the Depression Anxiety Stress Scale- Short form (DASS-21) (Lovibond & Lovibond, 1995). It is chosen as the primary outcome measurement because scales of anxiety and depression possess the capacity to differentiate from the related state of tension and stress linking with environmental demands and emotional and physical disturbance. It is a 21-item instrument that measures over the past week symptoms of depression, anxiety and stress rated by 4-point severity or frequency scale. The scale is from 0 (did not apply to me at all) to 3 (applied to me very much or most of the time). Internal consistency for each scale for the DASS normative sample are as follows: Depression $\alpha=0.91$; Anxiety $\alpha= 0.84$; Stress $\alpha=0.90$. The phi coefficients of the Chinese DASS-21 version are as follows: Beck Depression Inventory and Beck Anxiety Inventory are Depression-Anxiety 0.81; Anxiety-Stress 0.88 and Depression-Stress 0.83 (Moussa, Lovibond and Laube, 2001).

The secondary outcome measures will be including:

The Emotion Regulation Questionnaire (ERQ) (Gross and John, 2003) is a 10-item scale that was developed to measure participants' tendency to regulate their emotions in cognitive reappraisal and expressive suppression. Items are scored on a 7-point Likert scale ranging from 1 (strongly disagree) to 7 (strongly agree). The internal consistency reappraisal items are from $\alpha= 0.75 - 0.82$ while suppression items are from $\alpha= 0.68 - 0.76$. The reliability for reappraisal and suppression is $\alpha=0.79$ and $\alpha=0.73$ respectively.

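### Both arms are delivered in therapy groups, but the sample size and the repeated-measures ANOVA treat participants as independent, so the stated 80% power at a true 5% level is not assured

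*SAP*

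**What the plan says.** The Introduction states the primary hypothesis as "group Mindfulness-based Cognitive Therapy for Psychosis (MBCTp) plus treatment-as-usual (TAU), in comparison to active control group psychoeducation plus TAU". The Interventions section says that "MBCTp will be delivered to the study groups while PEp will be delivered to the control groups", in 12 weekly sessions, and that "Intervention groups will be facilitated by the researcher who is experienced in cognitive therapy and mindfulness". One research assistant runs the psychoeducation, so each arm has a single facilitator.

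The number and size of therapy groups are not stated. The nearest hint is the fidelity check, where "three to four sessions will be randomly audio-recorded per intervention group to make up a full program for progress evaluation". With 12 sessions in a program, this suggests three or four MBCTp groups but does not say so.

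On recruitment, the SAP says "The subjects will mainly be recruited from three service organizations and thus around 35 from each organization", and on allocation, "Simple randomization will be used to select subjects from the patient list in each organization". It does not say whether therapy groups are formed within organizations.

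Under Sample size, "Study power calculation indicated that 82 participants (n=41 per group) were required to detect statistically significant differences on emotional distress between two groups". The inputs given there are a standardised difference of 0.63, a 0.05 threshold and 80% power. The total is then raised to 95 (48 per group) for 15% attrition. Under Data Analysis, "Repeated-measures ANOVA tests will be used to assess any significant differences" within and between arms and across the three post-tests, with every test at the 5% level. No section gives an ICC, a design effect, a random effect or a term for therapy group or organization.

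**The concern.** People who attend the same 12 sessions share a room, a group dynamic and one another. If this makes their outcomes more alike, each extra group member adds less information than an independent person would. Repeated-measures ANOVA allows for correlation between one person's visits, not between members of one group. The standard error of the arm comparison would then be too small, its confidence interval too narrow and its false-positive rate above the stated 5%. The 80% power would be tied to a test that does not hold its level.

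**Working it through.** **1. The plan's own figure.** Inputs from Sample size: d = 0.63 (the mean of 0.76 and 0.50), alpha 0.05, power 0.80. A two-sided two-sample t-test on independent people needs 40.5 per arm, so 41 per arm and 82 in total. Power is 80.5% at 41 per arm and 79.5% at 40. The stated 82 is reproduced exactly, so it contains no allowance for clustering.

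**2. Effect of clustering at one time point.** Assumed, because the SAP is silent: ICC 0.01 to 0.05, m = 8 to 14 per group, no organization share, 41 analysed per arm.

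- Design effect: DE = 1 + (m − 1) × ICC
- Error of the unadjusted test: 2 × P(T80 > 1.990/√DE)
- Power of a test that holds 5%: noncentral t, df 80, noncentrality 0.63 × √(41/(2 × DE))

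For m = 10 and ICC 0.02: DE = 1 + 9 × 0.02 = 1.18; noncentrality = 0.63 × √(41/2.36) = 2.63; power 73.7%; error 7.1%.

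| ICC | DE, m = 8 to 14 | Error of unadjusted test | Power of a 5% test (upper bound) |
|---|---|---|---|
| 0.01 | 1.07-1.13 | 5.8-6.5% | 77.8-75.5% |
| 0.02 | 1.14-1.26 | 6.6-8.0% | 75.2-70.9% |
| 0.05 | 1.35-1.65 | 9.1-12.5% | 67.9-59.3% |

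The power column is an upper bound because it keeps 80 degrees of freedom, and a few groups supply far fewer. Even at ICC zero, a test on group-level degrees of freedom (2k − 2 for k groups per arm, organization not fitted) has 59% power with 3 groups of 14, 65% with 4 of 10 and 70% with 5 of 8.

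**3. Share due to organization.** Simulated error of the unadjusted test (40,000 runs, three organizations, one group of 14 per arm in each):

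| ICC | No organization share | Half | All |
|---|---|---|---|
| 0.01 | 6.5% | 5.8% | 4.9% |
| 0.02 | 8.3% | 6.5% | 4.9% |
| 0.05 | 12.8% | 8.7% | 4.5% |

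An organization effect is common to both arms and cancels from the comparison. Only correlation beyond it inflates the error.

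**4. Power of the test as planned.** In the same layout with no organization share, the unadjusted test still rejects in about 80%, 79% and 76% of simulated trials at ICC 0.01, 0.02 and 0.05 when d = 0.63. It does so at the inflated error rates of step 3.

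**5. Which contrast.** Data Analysis does not say which F-test decides. A therapy-group effect that arises after baseline inflates the between-arm effect, and also arm × time if baseline is a level of time. If time covers only the three post-tests and the group effect is constant over them, it subtracts out of arm × time, whose error stays near 5%. That test, however, has no power for a treatment effect that is also constant.

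**6. Attrition (separate).** 82/0.85 = 96.5, so 97; per arm 41/0.85 = 48.2, so 49 and 98 in total. The stated 95 matches 82 × 1.15 = 94.3 rounded up, and 2 × 48 = 96, not 95. Recruiting 95 leaves 95 × 0.85 = 80.75 analysed, with 79.5% power at 80 and 80.0% at 81, before any clustering.

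**The case against.** The size rests wholly on assumed inputs. The content is manualised and one facilitator per arm removes facilitator differences as a source of correlation within an arm, so the low end of the ICC range is plausible. There the error is 5.8-6.5%, and less with some organization share. This stands: the direction is conditional on a positive correlation, and the larger figures need ICC 0.05, large groups and no organization share.

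A reader might infer that the planned test has only 59-68% power. The documents do not support that. Those figures belong to a corrected test, and the planned one keeps about 76-80% with three groups of 14 per arm. Its fault is the error rate at which it does so.

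A reader might also infer that every reading of the ANOVA is inflated, or that the SAP fixes three or four groups per arm. Step 5 answers the first. The second is only an inference from the audio-recording sentence, for one arm.

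Finally, making a random-group model the sole primary analysis could cost a great deal. With three groups per arm and organization fitted, 2 degrees of freedom remain and power is 37% at ICC zero before baseline adjustment. This stands too, and it is why the fix depends on the number of groups. It does not justify leaving therapy group out of the plan altogether.

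**Conclusion.** The point holds in conditional form. The 82 and the ANOVA assume independent participants in a trial that treats both arms in groups, and the SAP gives no ground for assuming zero correlation within them. If that correlation is positive beyond organization, the between-arm test (and arm × time when baseline is a level of time) runs above 5%, and 80% power at a true 5% level is not delivered. The amount ranges from under one percentage point of extra error to about 7.5 points, over the assumed ICC of 0.01-0.05 and groups of 8-14. It vanishes if organization accounts for all the correlation. The attrition figure is a separate small error of two or three participants and adds no weight to the clustering point.

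**What to change.** **Sample size.** State the planned number and size of therapy groups per arm and whether they form within organizations. Restate power, leaving enrolment as it is, for a group-adjusted test over a stated ICC range such as 0.01-0.05.

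**Data Analysis.** Name the contrast that decides the primary outcome. Pre-specify a linear mixed model for DASS-21 at the three post-tests, with arm, time, arm × time, baseline DASS-21 and organization as fixed effects, repeated measures within participant, a random intercept for therapy group as assigned, Satterthwaite or Kenward-Roger degrees of freedom, and a fixed rule for a zero group-variance estimate. Make it primary if the layout gives enough groups, for example about six per arm. Otherwise report it as a pre-specified sensitivity analysis beside the primary result, with the ICC and its confidence interval, and qualify the conclusion if the two differ.

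**Attrition.** Either correct the total to 97 (98 if balanced, 49 per arm), or keep enrolment and state that 95 recruited leaves about 80-81 analysed. Remove the mismatch between 95 and 48 per group.

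**Cost.** The clustering changes are SAP wording and use data the trial will hold anyway: therapy-group assignment and organization. Intervals widen and the stated power looks less favourable. With organization fitted, six groups of seven per arm leave 8 degrees of freedom and 70-72% power at ICC zero, or 81-82% with baseline adjustment at an assumed correlation of 0.5. Three groups of 14 give 37%, or 52% if a zero variance estimate releases the degrees of freedom. No such model can separate the single facilitator in each arm from the treatment.
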